### **10.2 Data Management**

Data will be entered in the electronic data capture (EDC) system at the investigational site.

The data management plan will describe the methods used to collect, check, validate, and process clinical data in detail. It will also clarify the roles and responsibilities for the different functions and personnel involved in the data management process.

AEs and medical/surgical history will be classified according to the terminology of the Medical Dictionary for Regulatory Activities (MedDRA; version specified in the Data Management Plan). Medications will be classified according to the latest World Health Organization (WHO) Drug Dictionary.

Quality control procedures will be applied to each stage of data handling to ensure that all data are reliable and have been processed correctly. When all data have been coded, validated, and locked, clean file will be declared. Any treatment-revealing data may thereafter be added and the final database will be locked.

### **10.2.1 Audits**

In addition to monitoring, the Sponsor, Sponsor's representative, US or foreign regulatory authorities, and/or the reviewing IRB/ethics committee, may audit the conduct of the study. The auditors must have access to all study documents, the facilities where the study was conducted, and the study staff for interviews. The investigator will contact the Sponsor immediately if contacted by a regulatory agency about an inspection at the center.

## **11 Ethics**

The study will be performed in accordance with applicable regulatory requirements, the International Council for Harmonisation (ICH) guideline for Good Clinical Practice (GCP), and the ethical principles that have their origins in the Declaration of Helsinki.

An IRB will approve the final study protocol, including the final version of the informed consent form and any other written information and/or materials to be provided to the subjects, before any subjects are enrolled. The investigator will ensure the distribution of these documents to the applicable IRB/EC and to the staff of the study site.

### **11.1 Informed Consent**

Prior to performing any study procedures, written informed consent will be obtained from the subject. The method of obtaining and documenting the informed consent and the contents of the informed consent will comply with ICH-GCP and all applicable regulatory requirements.

## **12 Data Handling and Recordkeeping**

The investigator must keep the study documentation for 15 years after the completion of the study.

[figure not shown]
## **13 Publication Policy**

The Sponsor intends to publish the findings of the study and in general follows the guidelines set forth by the Internal Committee of Medical Journal Editors (ICMJE) (6). The investigator may publish the data from the site one year after the last participant finished the study.

### Visual Analog Scale

Please draw a **single vertical line** through the scale below that corresponds to the intensity (severity) of any pain you are feeling **right now**.

To indicate “no pain” or “worst possible pain” please **circle** the words instead of marking on the line.

No pain |—————| Worst possible pain

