### 2.1 Primary Objective

The primary objective is to characterize the safety and tolerability profile of escalating dose levels of EXT608 when administered to healthy adult participants as a single injection as assessed by:

1. Incidence, nature, and severity of adverse events (AEs) and withdrawals due to treatment emergent AEs (TEAEs) [Time Frame: Day 0 up to Day 28]
2. Frequency and severity of post-dose change from baseline in hematology, serum chemistries, urinalysis, electrocardiogram (ECG), vital signs, and physical examination (Exam) findings [Time Frame: Day 0 up to Day 28]
3. Percentage of participants with injection or infusion site reactions [Time Frame: Day 0 to Day 7]

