## **6.4 Injection Site Assessment**

The intended injection site in the abdomen will be photographed prior to injection.

The injection site assessment includes evaluation of erythema, edema and any tenderness. The size of any erythema is measured with shortest and longest size in mm, and edema similarly in size and in addition the tallest height above surrounding skin. The measurement data are recorded in the EDC.

Any positive finding will be photographed with clear labeling next to the lesion of participant ID, date and time.

Following a positive finding the injection site will be photographed daily in the inpatient period, and subsequently at the clinics visits until resolved.

Minimally, the photographs

1. prior to injection,
2. when the event is at highest intensity, and
3. when resolved or stabilized

will be uploaded in the EDC.

A Visual Analog Scale (VAS) will be used for evaluation of injection site pain. A copy of the VAS is in [Appendix 2](#).

Positive events will furthermore be recorded as AEs.

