## 6.9 Blood Sample Laboratory Variables

### 6.9.1 Blood Sample Draw

Blood is drawn either from a phlebotomy, or an indwelling catheter during the inpatient period after drawing out minimally 1 ml blood that is discarded per the investigational site's procedures.

Samples are drawn into appropriate sample container and processed according to the laboratory's instructions.

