#### 3.3.4.5 *Injection site reaction*

## EXTBIO EXT608-101 Statistical Analysis Plan, V2, 2023-JULY-04

Injection site Assessment includes Tenderness, VAS pain score, Edema and Erythema.

- If Tenderness is “None” and VAS pain score is missing, then VAS pain score will be set as 0
- No substitution will be done for any missing VAS if Tenderness is not None.

Although the standard VAS line is 100mm, the actual VAS line printed on paper could be deviate from 100mm due to printer settings. Thus, all reported VAS will be normalized to 100mm scale for analyses.

The normalized VAS ( $VAS_{nom}$ ) score is calculated as below:

$$VAS_{nom} = \frac{Measured\ VAS(mm) \times 100}{Total\ VAS(mm)}$$

The following describes the handling of Edema and Erythema related variables.

- If “none” reported for edema or Erythema, then the following variables will be substitute as 0 for analyses only
  - Shortest length (Edema or Erythema)
  - Longest length (Edema or Erythema)
  - Tallest height (Edema)
  - Grade (Erythema)
- If “not done” reported, there is no substitution

Edema and Erythema is assumed to be Ellipse, and the area will be calculated as:

$$Area\ of\ Edema\ or\ Erythema = \frac{(3.14159 \times \text{shortest\ length} \times \text{longest\ length})}{4}$$

The Grade of Erythema is expected to be the following:

- 1: very faint, 2: faint, 3: bright, 4: very bright
- If a non-integer number is reported, it will be rounded to the nearest integer.

The tallest height of Edema will be used directly.

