**3.4.5.5 *Injection site reaction***

Injection site reactions include VAS, tenderness, Edema and Erythema. The parameters defined in section 3.3.4.5 will be summarized descriptively by each treatment arm.

EXTBIO EXT608-101 Statistical Analysis Plan, V2, 2023-JULY-04

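### The VAS is meant to measure injection site pain, but the Appendix 2 form asks about any pain and names no body site, so pain elsewhere can enter the injection site VAS summaries.

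*Protocol*

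**What the plan says.** Protocol 6.4 gives the purpose of the scale: "A Visual Analog Scale (VAS) will be used for evaluation of injection site pain". It refers to Appendix 2 for the form itself.

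The form in Appendix 2 asks for one vertical line at the point "that corresponds to the intensity (severity) of any pain you are feeling" at the time of completion. Its two ends are no pain and the worst pain possible. Neither the abdomen nor the injection appears in the instruction.

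The SAP treats the score as local. Section 3.3.4.5 states "Injection site Assessment includes Tenderness, VAS pain score, Edema and Erythema", and section 3.4.5.5 states "Injection site reactions include VAS, tenderness, Edema and Erythema" and summarizes these parameters descriptively by arm. One SAP rule links the VAS to local tenderness: "If Tenderness is “None” and VAS pain score is missing, then VAS pain score will be set as 0". A missing VAS with tenderness present is left missing.

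Two other provisions bear on the consequence. One primary measure in Protocol 2.1, repeated in SAP 1.2.1, is "Percentage of participants with injection or infusion site reactions [Time Frame: Day 0 to Day 7". Protocol 6.4 ends with "Positive events will furthermore be recorded as AEs".

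**The concern.** The form and its stated use ask different questions. A participant who reads the form literally reports all pain present at that moment. The analysis then labels the whole score as pain at the injection site.

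Other pain is plausible here. Participants are confined for four nights with serial sampling, and Protocol 6.9.1 says "Blood is drawn either from a phlebotomy, or an indwelling catheter during the inpatient period". Headache is another ordinary example.

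Two distortions of the VAS summaries could follow. If EXT608 caused a systemic pain that rose with dose, the summaries would show what looks like dose-related local intolerance. If background pain were unrelated to treatment, it would add noise to every arm and blur any real local difference from pooled placebo. The form records no location, so the score alone cannot be sorted out afterwards.

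**Working it through.** The plan states no figure on this point, so there is nothing to reproduce. The check is a comparison of texts, followed by an illustration.

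**Step 1: what each place asks for or assumes.**

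| Place | What the VAS is |
|---|---|
| Protocol 6.4 | A measure of injection site pain |
| Protocol Appendix 2 | Any current pain, no site named |
| SAP 3.3.4.5 | One of four parts of the injection site assessment |
| SAP 3.4.5.5 | Listed among injection site reactions, summarized by arm |

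Only the second row is seen by the participant, and it does not match the other three.

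**Step 2: does the SAP correct for this later?** The tenderness rule acts only when the VAS is missing. A recorded VAS above 0 with tenderness 'None' stays in the summary unchanged. The SAP defines a baseline for vital signs, ECG, laboratory and PD variables, weight and physical exam, but none for the VAS, so pain already present before dosing is not removed. The only transformation is scaling to 100 mm.

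**Step 3: does the score reach the primary percentage or the adverse events?** No section sets a VAS cut-off or turns the score into a yes/no reaction. SAP 3.4.5.5 summarizes the parameters and does not define a participant with a reaction. In Protocol 6.4 the assessment is first described through erythema, edema and tenderness, and positive findings are photographed as lesions. The VAS sentence comes later, just before the sentence on recording positive events as adverse events. Whether a VAS mark alone is a positive event is left open.

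**Step 4: possible size in the VAS summaries.** With three active participants per cohort (Protocol 8.1), a mark of x mm by one of them moves that arm's mean by x/3 mm and, if the other two score 0, sets the maximum to x while the median stays 0.

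Let p be the chance that a participant has some pain away from the site at one rating. The documents give no value, so 5%, 10% and 20% are assumed. With independent participants, the chance that at least one of n has a non-zero score from that pain alone is 1 − (1 − p)^n. For n = 6 (one placebo participant in each of six cohorts) this refers to the pooled placebo group.

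| p | n = 3 active in a cohort | n = 6 pooled placebo |
|---|---|---|
| 5% | 1 − 0.95^3 = 14% | 1 − 0.95^6 = 26% |
| 10% | 1 − 0.90^3 = 27% | 1 − 0.90^6 = 47% |
| 20% | 1 − 0.80^3 = 49% | 1 − 0.80^6 = 74% |

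These are chances of a non-zero score at one rating. They are not reaction rates.

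**The case against.** The strongest reply is that the context of use narrows the question. Protocol 6.4 introduces the scale for injection site pain, and the amendment history gives its purpose as standardizing the measurement of tenderness. The SAP's zero-filling rule would fit a practice of skipping the form when there is no tenderness. Staff may point participants to the site. The schedules and most of the stepwise procedures in Protocol 7.1 and 7.2 are not visible in the public text, so such an instruction could exist there. This stands as a limit on how often other pain would be scored. It does not remove the mismatch, because no visible text restricts the rating and a self-completed form is standardized only by what is printed on it.

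The reply is stronger on consequences. A reader might infer that a headache marked on the form becomes an injection site reaction in the primary percentage, so that one affected participant of three adds 33 percentage points (1/3). The documents do not support this: it needs a rule that any mark above 0 is a reaction, and there is none. A reader might also infer that the mark generates an injection site adverse event. Nothing directs this either. Protocol 6.10.1.1 requires each event to be described and assessed for causality, so a headache would ordinarily be recorded as a headache.

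It is also tempting to compound the illustration over repeated ratings. The visible text does not give the number of VAS ratings, and pain at nearby times in one person is correlated, so a calculation that assumes independent ratings would overstate the risk.

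Finally, the other three components are assessed separately, the trial is double-blind, and no formal hypothesis testing is planned in the protocol. These points limit the damage but do not make the VAS summaries interpretable as local pain.

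**Conclusion.** The mismatch is real and lies in the current text. Followed as printed, the form measures pain anywhere in the body, and the SAP reports the result by arm as an injection site parameter with no correction for location or baseline. Pain elsewhere can therefore enter the injection site VAS summaries.

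Any effect on the primary percentage or on adverse event recording is conditional on treating a non-zero VAS alone as a positive finding. The plan should settle that question and does not. Tenderness, erythema and edema are unaffected.

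The size cannot be derived from the documents. The 14% to 49% range for a cohort's three active participants rests on the assumed 5% to 20% background pain, on independence between participants, on literal reading of the form, and on the form being completed whether or not the site is tender. The conclusion does not depend on that range. This is a measurement defect in one component of a safety assessment, worth correcting because the correction is small.

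**What to change.** - **Appendix 2:** reword the instruction so that it asks only for pain felt right now at the place on the abdomen where the study injection was given.
- **SAP 3.3.4.5, listing:** list all records with VAS above 0 and tenderness 'None'. Do not exclude them: some may be genuine spontaneous pain at the site, and the form gives no location on which to base an exclusion.
- **SAP 3.3.4.5, definition:** state before unblinding whether a VAS score alone counts as an injection site reaction, and make Protocol 6.4 consistent with that statement.
- **SAP 3.4.5.5:** show scores collected on the current form separately from scores collected on the reworded form.

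The cost is one sentence on a form, a minor protocol amendment and a short SAP revision. The downside is that scores from the two forms are not directly comparable, which divides already small groups. If all scores have already been collected on the current form, the listing and the definition can still be added, and the tables should then label the VAS as pain at any site.

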## ABBREVIATION AND DEFINITIONS

- **$\lambda_z$** : Terminal rate constant
- **ADA**: Anti-drug Antibodies
- **AE**: Adverse Event
- **ANOVA**: Analysis of Variance
- **AUC**: Area under the curve
- **AVG**: Average
- **CMax**: Maximum Concentration
- **CL/F**: Clearance
- **DIABP**: Diastolic Blood Pressure
- **ECG**: Electrocardiogram
- **EDC**: Electronic Data Capture systems
- **EXT608**: Name of the study medication
- **FAS**: Faull Analyses Set
- **FIH**: First-in-human
- **LLOQ**: Lower limit of quantification
- **MedDRA**: Medical Dictionary for Regulatory Activities
- **Nab**: Neutralizing subset
- **PD**: Pharmacodynamics
- **PK**: Pharmacology
- **PP**: Per Protocol
- **PT**: Preferred Term
- **SAD**: Single Ascending Dose
- **SAE**: Serious Adverse Event
- **SAS**: Analyses Software by SAS institute
- **SOC**: System Organ Class
- **SYSBP**: Systolic Blood Pressure
- **TMax**: Time corresponding to the Maximum Concentration
- **tHalf,early**: Half-life Early
- **tHalf,late**: Half-life Late
- **VAS**: Visual Analogue Scale
- **Vz/F**: Volume Distribution
- **V**: Volume

## EXTBIO EXT608-101 Statistical Analysis Plan, V2, 2023-JULY-04

# 1 OVERVIEW

## 1.1 INTRODUCTION

This documentation describes the planned data analyses for Extend Biosciences EXT608-101 clinical trial.

## 1.2 OBJECTIVES

### 1.2.1 Primary Objective

The primary objective is to characterize the safety and tolerability profile of escalating dose levels of EXT608 when administered to healthy adult participants as a single injection as assessed by:

- Incidence, nature, and severity of adverse events (AEs) and withdrawals due to treatment emergent AEs (TEAEs) [Time Frame: Day 0 up to Day 28]
- Frequency and severity of post-dose change from baseline in hematology, serum chemistries, urinalysis, electrocardiogram (ECG), vital signs, and physical examination (Exam) findings [Time Frame: Day 0 up to Day 28]
- Percentage of participants with injection or infusion site reactions [Time Frame: Day 0 to Day 7]

### 1.2.2 Secondary Objectives

The secondary objectives are to assess:

- Single dose PK including AUC0-24h, AUC0-48h, AUC0-28d, AUC0-∞, Cmax, Tmax, T1/2, λz, Cl/F and Vz/F.
- Single dose PD by post-dose change from baseline in serum chemistries with particular attention to Se-Ca, phosphate, magnesium, and creatinine. Urinalysis will also be performed.

### 1.2.3 Exploratory Objectives

Furthermore, the exploratory objectives are to assess:

- Single dose Immunogenicity by anti-drug antibodies (ADA) and any neutralizing subset (NAb),
- Single dose effect on vitamin D metabolism by serum 25-hydroxy-vitamin D and 1,25-dihydroxy-vitamin D concentrations.

## 1.3 ANALYSIS SOFTWARE

SAS 9.4 Windows

EXTBIO EXT608-101 Statistical Analysis Plan, V2, 2023-JULY-04

**1.4 MODIFICATIONS FROM THE STATISTICAL SECTION IN THE PROTOCOL**

None

## EXTBIO EXT608-101 Statistical Analysis Plan, V2, 2023-JULY-04

## 2 INVESTIGATIONAL PLAN

### 2.1 STUDY DESIGN AND RANDOMIZATION

[figure not shown]
#### 2.1.1 Study Design

This is a randomized, double-blind, first-in-human (FIH), placebo-controlled single ascending dose (SAD) study to study the safety, tolerability, PK, and PD of EXT608 in healthy adult participants.

This is a multiple cohort study. Participants will be enrolled into 1 of up to 6 planned single dose cohorts (designated as S1 through S6, respectively) in ascending fashion.

- Each cohort will consist of 4 participants randomized to receive either EXT608 or placebo, whereby 3 will receive a single injection of EXT608 and 1 will receive matching placebo.
- Up to approximately 30 participants may be enrolled to the study intervention such that approximately 24 evaluable participants complete the study.
- Participants who discontinue prematurely may be replaced at the discretion of the Sponsor.
- Additional participants and cohorts may be enrolled pending review of study data and recommendation by a Data Monitoring Board (DMB) and ratification by the Sponsor.

**Figure 1 Study Design**

## EXTBIO EXT608-101 Statistical Analysis Plan, V2, 2023-JULY-04

### 2.1.2 Randomization

Treatment allocation is performed in the EDC in a manner that ensures only the unblinded pharmacist or unblinded monitoring person know the treatment code. The treatment assignment is computer generated by the EDC at the point of randomization.

- Participants are randomized 3:1 EXT608:Placebo in blocks of 4.
- A Pocock-Simon (Pocock and Simon 1975) allocation minimization procedure is implemented into the randomization process to ensure the balance between each treatment arm.
- The balance procedure is based on the serum calcium (mg/dL) obtained at visit Day -1 of each participant.
- Participants who discontinue prematurely may be replaced at the discretion of the Sponsor.

### 2.1.3 Sample Size Justification

The sample size is not determined for inferential testing purposes. The sample size of 4 participants per cohort (3 EXT608: 1 Placebo) is considered sufficient for evaluation of safety, tolerability, and PD of EXT608 prior to making a decision about dose escalation as Se-Ca is very tightly regulated and determination of effect based on simulations can therefore reliably be made with the small sample.

EXTBIO EXT608-101 Statistical Analysis Plan, V2, 2023-JULY-04

### **3 Statistical and analytical procedures**

#### **3.1 ANALYSIS POPULATIONS**

Two participant populations are defined.

##### **3.1.1 Safety or Full Analysis Set population (FAS)**

The Safety or Full Analysis Set population (FAS) will be defined as all participants who are randomized.

- In the event of subjects having received treatments that different from those assigned according to the randomized schedule, then the safety analyses will be conducted according to the treatment received rather than according to the randomization groups.
- Participants who are replaced and received at least one study medication will also be included in this population.

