### 8.2 Analysis populations

Two participant populations will be defined. The Safety of Full Analysis Set population (FAS) will be defined as all participants who are randomized. The Per-Protocol (PP) population will be participants for whom evaluable data to and including Day 7 is available and with no major protocol violations.

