### 8.3 Data Analysis

AEs will be presented in listings and Treatment Emergent Adverse Events (TEAEs) will be summarized. Individual results of laboratory tests (hematology, chemistry, and urinalysis) will be listed and change from baseline will be summarized using shift tables. Individual results of vital signs will be listed and observed values and changes from baseline will be summarized.

Individual results of quantitative ECG parameters from the 12-lead safety ECGs will be listed and observed values and changes from baseline will be summarized and analyzed consistent with the ICH E14 (3).

All summaries will be performed by placebo and each EXT608 dose level. Placebo data will be pooled across cohorts. Physical exam findings will be presented in data listings.

Concentrations of EXT608 will be summarized by dose over each scheduled sampling time using descriptive statistics. Individual plasma concentration data versus time will be presented in a data listing. PK parameters will be summarized by dose using descriptive

statistics. Dose proportionality will be assessed graphically and using a power model. PD will be presented in listings and summarized by dose and time point.

Detection of ADA and NAbs will be presented in listings and summarized by dose and time point.

No formal hypothesis testing will be conducted as part of this study.

DMB data packages will be based on the FAS for safety and PP for PK/PD.

Further details are described in the Statistical Analysis Plan.

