## EXTBIO EXT608-101 Statistical Analysis Plan, V2, 2023-JULY-04

**3.3.1.1 Age**

Since only the month and year of birth are collected in the EDC, we will use number 15 to substitute the day of birth.

Then the Age will be calculated by:

$$\text{Age} = \text{Floor}\left(\frac{\text{Day 0} - (\text{The approximated Date of Birth})}{365.25}\right)$$

- Function floor means age will take the largest integer (e.g., age 50.8 will become age 50).
- For participant who is not advanced to Day 0, i.e. screening failure or randomized but not dosed, there will be no Age calculated.

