### 3.3.4 Safety Variables

#### 3.3.4.1 *Adverse Events (AE)*

All observed or volunteered adverse events regardless in the treatment group or suspected causal relationship to the investigational device are captured in the EDC.

For all AEs, reformatting maybe applied and necessary transformation/Substitution may be needed as specified below:

- If an AE has known onset date but unknown onset time, then 12:00 will be used to substitute the onset time
  - The purpose of this substitution is for the determination of the TEAE
- If an AE has unknown onset date, no substitution will be done.

Treatment-emergent adverse event (TEAE) is defined as a post-baseline adverse event with onset date and time after the initiation of study treatment.

- Baseline is the IP administration date and time
- In this study, TEAE are the AEs that occur after the first successful IP administration.
  - If the AE has an unknown onset date, it will be assumed to be non-TEAE unless the investigational site confirms it is an TEAE

AE Coding:

- AE will be coded with latest available, at the time of coding, MedDRA code.

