### **3.4.5 Safety Analyses**

All Safety analyses will be done for Safety/FAS population.

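### The only safety population is all randomised participants, so anyone randomised but not dosed dilutes the adverse-event percentages of their arm

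*SAP*

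**What the plan says.** SAP 3.1.1 defines the set in one sentence: "The Safety or Full Analysis Set population (FAS) will be defined as all participants who are randomized". Protocol 8.2 agrees: the set "will be defined as all participants who are randomized". The only other population in either document is per-protocol, so there is no dosed-only set.

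This set carries the safety reporting. SAP 3.4.5 states: "All Safety analyses will be done for Safety/FAS population". Protocol 8.3 adds: "DMB data packages will be based on the FAS for safety and PP for PK/PD".

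Two bullets follow the SAP definition. One says that participants who got a treatment other than the assigned one are analysed for safety as treated. The other says: "Participants who are replaced and received at least one study medication will also be included in this population". Protocol 8.2 has neither bullet.

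SAP 3.3.4.1 ties a TEAE to dosing: "In this study, TEAE are the AEs that occur after the first successful IP administration". SAP 3.4.5.1 reports TEAEs as the count and per cent of participants affected, with events as counts only; these tables are produced if the study has more than 5 TEAEs. SAP 3.3.1.1 foresees participants who never receive product: for someone "randomized but not dosed, there will be no Age calculated".

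**The concern.** A participant who received no study product cannot have a TEAE under the SAP's own definition, but is in the population on which TEAE percentages are based. Such a person can only pull the percentage down. Incidence of adverse events is part of the primary objective, and a dose level has 3 active participants, so one extra person in the denominator is visible.

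The shift is also unequal between groups. One undosed participant moves a 3-person dose level more than a 6-person pooled placebo group, so the side-by-side comparison can be distorted.

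The definition fits poorly with other SAP rules. Day 0 is the date of dosing (SAP 3.3.2.1), so an undosed member of the safety set has no Day 0 from which to count the Day 0 to Day 28 window. Age is summarised on the same set (SAP 3.4.3) but is not calculated for that person.

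**Working it through.** **Inputs**

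- Up to 6 cohorts of 4, each with 3 on EXT608 and 1 on placebo; about 24 evaluable (Protocol 3.1.1).
- Placebo pooled across cohorts (Protocol 8.3).
- TEAE only after dosing (SAP 3.3.4.1); percentage of participants reported (SAP 3.4.5.1) on the Safety/FAS set (SAP 3.4.5).
- Number randomised but not dosed: not given. Assumed here to be 1 or 2 in a group; with 0 there is no effect.

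**Step 1: the plan's own count.** 6 × 4 = 24, of which 6 × 3 = 18 active and 6 × 1 = 6 placebo. This matches the stated target of about 24. There is no power calculation to reproduce, since SAP 2.1.3 says that the size was not set for inference.

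**Step 2: formula.** Let d be the number dosed in a group, u the number randomised but undosed, and x the number with a TEAE. The dosed-only percentage is x/d. The percentage as the plan defines it is x/(d + u). For x > 0 the relative fall is 1 − [x/(d + u)]/[x/d] = u/(d + u), whatever x is.

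**Step 3: numbers.** Here the planned number has been dosed, so the undosed person is additional, as after a replacement.

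| Group | d | u | Dosed only | All randomised | Relative fall |
|---|---|---|---|---|---|
| Dose level | 3 | 1 | 1/3 = 33.3% | 1/4 = 25.0% | 25.0% |
| Dose level | 3 | 1 | 2/3 = 66.7% | 2/4 = 50.0% | 25.0% |
| Dose level | 3 | 2 | 1/3 = 33.3% | 1/5 = 20.0% | 40.0% |
| Pooled placebo | 6 | 1 | 1/6 = 16.7% | 1/7 = 14.3% | 14.3% |
| All EXT608 | 18 | 1 | 1/18 = 5.6% | 1/19 = 5.3% | 5.3% |

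If the undosed person is not replaced, a dose level has d = 2 and u = 1, and 1/2 = 50.0% becomes 1/3 = 33.3%.

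**Step 4: what does not move.**

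- With u = 0 the two definitions give the same figures.
- With x = 0 the percentage is zero either way.
- Event counts and the percentages of other arms are unchanged.
- Laboratory, vital-sign and ECG summaries use recorded values. Missing data are not estimated (SAP 3.2.1) and N is shown (SAP 3.4.1), so someone with no post-dose value does not enter a post-dose mean.
- Injection-site items marked as not done get no substitution (SAP 3.3.4.5). The denominator of the injection-site percentage is not stated, so the effect there cannot be settled.
- The escalation rules in Protocol 3.1.5 use counts of related Grade 3 events and average peak serum calcium, not these percentages.

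**Step 5: the bullet on replaced participants.** If all randomised participants are in the set, a bullet that also admits replaced participants who were dosed adds nobody. If the bullet is meant to do something, it suggests that replaced, undosed participants stay out, which the definition sentence contradicts. From the same data, one programmer could report 1/4 and another 1/3.

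**The case against.** The strongest reply is that the bullet on replaced participants shows that a dosing condition was intended, and the table above illustrates exactly that case. This stands in part: for replaced, undosed participants the fair charge is that SAP 3.1.1 is unclear. But the bullet excludes no one expressly, Protocol 8.2 has no such bullet, and an undosed participant who is not replaced is in the set on any reading.

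A second reply is that the situation should be rare. Treatment is a single injection, admission is one day before dosing, and allocation uses the Day -1 serum calcium (SAP 2.1.2), which suggests randomisation close to dosing. Under sentinel staggering (Protocol 3.1.3) the last participants are dosed only if earlier reviews raise no concern, but that leaves someone undosed only if they were already randomised. The readable text does not settle the timing. The Age rule covers a contingency and does not show that the sponsor expects it.

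A third reply is that harm is limited. Counts stand beside percentages, all adverse events are listed, disposition shows treatment randomised and received (SAP 3.4.2), and no test is applied to adverse events. A careful reader could recover the dosed denominator. That limits the seriousness, but does not make the percentage right.

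A reader might infer several stronger things that the documents do not support:

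- **Every adverse-event rate falls.** Only non-zero participant percentages in the affected arm or total do.
- **Escalation decisions are biased.** The rules do not use these percentages, and the detailed contents of the board's package are left to a safety plan outside these documents.
- **The allowance of about 30 enrolled for about 24 evaluable implies about 6 undosed.** Replacement covers anyone without reliable Day 7 data (Protocol 4.4), including people who were dosed and dropped out.
- **The as-treated bullet clashes with the definition.** It applies only to those who received a different treatment and says nothing about those who received none.

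**Conclusion.** The point holds, with a narrow and conditional effect. A stated rule, not a missing detail, places any randomised but undosed participant in the TEAE denominator with a certain zero in the numerator. One such person costs a 3-person dose level a quarter of its non-zero TEAE percentages and pooled placebo one seventh.

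This assumes that at least one participant is randomised and not dosed, that the SAP's percentages take the Safety/FAS count as denominator (the natural reading of SAP 3.4.5), and, for replaced participants, that the definition sentence prevails over the bullet. It should be corrected, because the percentages concern the primary objective and the wording permits two answers from the same data. It does not threaten the escalation rules.

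**What to change.** - Define the Safety Set, in SAP 3.1.1 and Protocol 8.2, as all randomised participants who received study product, analysed by treatment received.
- Use it for all safety tables and for the Data Monitoring Board safety package.
- Keep all randomised participants for disposition, and list there anyone not dosed.
- Reword the second bullet of SAP 3.1.1 to match: replaced participants who were dosed are in the Safety Set, and those who were not dosed appear in disposition only.
- State the denominator of the injection-site reaction percentage.
- SAP 1.4 records no departures from the protocol's statistical section. If Protocol 8.2 is not amended at the same time, log the change there.

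The cost is a few sentences across the two documents and no new data. It is best done before unblinding.
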